## CONFIDENTIAL AND PROPRIETARY

This document contains information that is confidential and proprietary to Smith & Nephew PLC and Smith & Nephew, Inc. and is intended for use only by Smith & Nephew and its manufacturer. It shall not be reproduced or copied in whole or in part, nor shall the contents be disclosed by any means without prior written permission from Smith & Nephew, nor shall anyone make any use of it that is contrary to the expressed or implied wishes of Smith & Nephew.

[REDACTED] - [REDACTED] - [REDACTED]

**Smith+Nephew****Clinical Protocol - Device****Pre-Registration Clinical  
Study**

Study Number:  
CT1705POB  
Version: 9.0 04Aug2021  
Page: 90 of 221

per specialty are needed to achieve sufficient statistical power for each specialty to be analysed separately, within this study.

Based on the above, a total of 88 subjects will be recruited, which will include 44 subjects with each of the following specialties: orthopaedics (closed surgical knee incisions, e.g. after total knee arthroplasty), and abdominal surgery (e.g. closed surgical abdominal incisions of which at least 50% would be colorectal cases).

For the management of exudate, measured by incidence of exudate leakage, the sample size is evaluated for adequacy based on the non-leakage rate recorded by the NWPT system. According to internal data collected within Smith and Nephew surgical study involving Closed Abdominal and Orthopaedic subjects, 85% of the PICO NPWT systems had no exudate leaks. Therefore, assuming that [REDACTED] NWPT system will manage 85% of exudate effectively or better, demonstrated through no exudate leakage observed, a sample size of 10 subjects for each specialty will be sufficient to exclude a response rate of 65% or less with 80% power by using a 2-sided 95% confidence interval for orthopaedics (closed knee incisions e.g. after Total Knee Arthroplasty), and Abdominal surgery (closed abdominal surgical incisions) separately. With the planned 44 subjects per specialty, a response rate below 70% could be excluded for each specialty individually.

For the dressing wear time (in days) the sample size is based on comparison of the [REDACTED] [REDACTED] system compared to the literature derived value for each specialty separately. The mean dressing wear time derived from literature is 4.6 days and a standard deviation of 2.2539. It is projected that the [REDACTED] NWPT system will have a mean dressing wear time of 7 days with similar distribution to the literature value.

The following hypotheses will be tested, for each specialty separately, to establish that the dressing wear time of the [REDACTED] [REDACTED] system is strictly not worse (lower) than the literature derived value:

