## **Clinical Protocol - Device**

### **Pre-Registration Clinical Study**

Study Number:  
CT1705POB  
Version:9.0 04Aug2021  
Page: 85 of 221

95% CI separately for each specialty. For each specialty, the non-leakage proportion for the study will be tested using the Exact test to establish if it is different from the literature derived value of 85% projected. Further, the resulting lower limit of 95% CI for each specialty will be evaluated to establish if it excludes values of 65% and below.

Composite Clinical Success (CCS) defined as a binary variable (1/0) (1 if all three of the following are true and 0 if at least one of the three is false):

- A. Average negative pressure within therapeutic range (-100mmHg to -60mmHg)
- B. Dressing wear time is 7 days
- C. No exudate leakage

The Composite Clinical Success (CCS) will be reported as a count and percentage with a 95% CI separately for each specialty.

A logistic model will be used to evaluate the adjusted and the un-adjusted models for the CCS primary outcome variable for each specialty, separately. The variables considered important and to be included in the final model are Age, Diabetic status and the presence of any other co-morbidity as a binary variable. All other baseline and medical factors collected at baseline will be evaluated for importance in adjusted models and only those statistically significant in an un-adjusted model will be considered in the final model.

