Based on the data used for sample size estimation, thirty eight (38) subjects are required to achieve 80% power to detect equivalence at the significance level of  $\alpha = 0.025$  (one-sided) within 7mmHg using a two-sided t-test. Drawing from past experience, allowing that 15% of the subjects may be lost to follow up by the end of the study, a sample size of 44 subjects

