**CONFIDENTIAL AND PROPRIETARY**

This document contains information that is confidential and proprietary to Smith & Nephew PLC and Smith & Nephew, Inc. and is intended for use only by Smith & Nephew and its manufacturer. It shall not be reproduced or copied in whole or in part, nor shall the contents be disclosed by any means without prior written permission from Smith & Nephew, nor shall anyone make any use of it that is contrary to the expressed or implied wishes of Smith & Nephew.

[REDACTED] - [REDACTED] - [REDACTED]

**Clinical Protocol - Device****Pre-Registration Clinical  
Study**

Study Number:  
CT1705POB  
Version:9.0 04Aug2021  
Page: 92 of 221

The 2nd phase of the study (post-interim analysis) will be powered according to previous sample size. However, as no further subjects will be recruited for the orthopaedic surgery group, all 44 subjects recruited will be in the abdominal indication group. This will increase the total number of abdominal incisions to 66 (22 recruited following the protocol v7.0 and 44 following v8.0 of the protocol). This ensures that the primary endpoint is sufficiently powered for both the primary analysis of the abdominal data for all subjects as well as for a secondary analysis to be done on the data from those recruited according to protocol v8.0 only.

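### Section 11.1 credits 10 subjects with 80% power to exclude a 65% non-leakage rate; the power is about 20% (exact or Wilson interval) or 54% (Wald)

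*Combined protocol and SAP*

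**What the plan says.** Section 11.1 takes its planning rate from the sponsor's internal data, in which "85% of the PICO NPWT systems had no exudate leaks". On that basis it states that "a sample size of 10 subjects for each specialty will be sufficient to exclude a response rate of 65% or less with 80% power". The interval behind this claim is two-sided at the 95% level. The section adds that the planned 44 per specialty could exclude a rate below 70%.

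Section 10.4.1 makes the 65% limit part of the analysis: "the resulting lower limit of 95% CI for each specialty will be evaluated to establish if it excludes values of 65% and below". The same paragraph says that "the non-leakage proportion for the study will be tested using the Exact test", but for a different comparison, against 85%. It does not name the type of interval for the 65% check.

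Section 11.2 carries the earlier sample size into phase 2 and describes the primary endpoint as "sufficiently powered for both the primary analysis of the abdominal data for all subjects as well as for a secondary analysis to be done", the latter in the version 8.0 subjects alone. That means 66 abdominal subjects in total, 44 of them in the subset.

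**The concern.** Ten subjects is very few for separating 85% from 65% with a 95% interval, because one leak already moves the observed rate by ten percentage points. Section 11.1 gives the same number, 10, for wear time, where the effect is large relative to its standard deviation. That is a reason to check whether it also suits leakage.

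Exudate management is one of the three primary components, and its 65% limit will be checked in the analysis. If the stated power is wrong, 44 subjects look like more than four times what this component needs. The section 11.2 assurance about the subset then appears to have a margin that it does not have.

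**Working it through.** **Inputs.** True non-leakage rate p1 = 0.85, excluded rate p0 = 0.65, n = 10 and a two-sided 95% interval, all from section 11.1. The 65% check is in section 10.4.1.

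**Formula.** Power = P(lower 95% limit > 0.65), with X ~ Binomial(n, 0.85) leak-free subjects. It is the sum of the binomial probabilities over every X whose lower limit clears 0.65.

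**The plan's own figure, n = 10.** Lower limits:

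| Leak-free | Exact | Wilson | Wald |
|---|---|---|---|
| 10/10 | 69.2% | 72.3% | 100% |
| 9/10 | 55.5% | 59.6% | 71.4% |
| 8/10 | 44.4% | 49.0% | 55.2% |

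- Exact and Wilson need 10/10: 0.85^10 = 0.197.
- Wald needs at least 9/10: 0.197 + 10 × 0.85^9 × 0.15 = 0.197 + 0.347 = 0.544.

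The stated 80% is not reproduced. Jeffreys, Agresti-Coull and mid-P intervals also give 19.7%. A 90% interval gives at most 54.4%. Two-sided normal approximations give 20% to 43% at n = 10, and the two-sided arcsine method gives 32%.

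The nearest figure is P(X ≥ 8) = 82.0%. At 8/10, however, no 95% interval excludes 65%, and that rule would pass a device with a true rate of 65% in 26% of trials.

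**Does a rate better than 85% rescue it?** With the exact or Wilson interval, 80% power at n = 10 needs p^10 = 0.80, so p = 0.80^(1/10) = 97.8%.

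**Where 10 does fit.** For wear time the difference is 7 − 4.6 = 2.4 days, with SD 2.25 and one-sided alpha 0.025. The noncentral t gives 79.98% power at n = 9 and 85.0% at n = 10. The number is sound for that endpoint.

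**Power to exclude 65% at the sizes that matter (true rate 85%).**

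| Evaluable n | Fewest leak-free needed (exact) | Exact | Wilson | Wald |
|---|---|---|---|---|
| 10 | 10 | 19.7% | 19.7% | 54.4% |
| 22 | 19 | 57.5% | 57.5% | 77.4% |
| 37 | 31 | 68.5% | 81.9% | 90.8% |
| 38 | 31 | 79.9% | 79.9% | 89.4% |
| 44 | 36 | 79.4% | 88.6% | 88.6% |
| 56 | 44 | 93.2% | 93.2% | 96.6% |
| 66 | 51 | 96.8% | 96.8% | 98.4% |

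The rows 37 and 56 apply the plan's loss allowance ("allowing that 15% of the subjects may be lost to follow up by the end of the study"): 44 × 0.85 = 37.4 and 66 × 0.85 = 56.1. The row 38 is the evaluable number that section 11.1 requires for pressure.

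**Size needed for 80%.** Power moves in a sawtooth as n grows; the exact values are 84.8% at 41, 81.3% at 43, 79.4% at 44 and 87.3% at 45. The n that first reaches 80% is 41 (exact), 37 (Wilson) or 26 (Wald). The n from which power stays at or above 80% is 45, 40 or 34. As a cross-check, the two-sided normal approximation gives n = [(1.960 × √(0.65 × 0.35) + 0.842 × √(0.85 × 0.15)) / 0.20]² = 38.15, so 39.

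**The adjacent 70% sentence.** The exact lower limit is 72.6% at 38/44 and 69.9% at 37/44. Exact power to exclude 70% is 50% at 44, 67% at 56 and 82% at 66.

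**The case against.** The arithmetic for n = 10 is not in dispute. The case on the other side is that little follows from it.

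- **Nothing uses the 10.** Enrolment came from the pressure calculation, which needs 38, and the leakage paragraph only checks adequacy. This stands. It limits the severity but does not make the sentence true.
- **Section 11.2 is not shown to be wrong.** It rests on 44 rather than 10, the subset analysis is secondary, and 79% to 89% power is at or near 80%. This stands for 44 evaluable subjects. What remains is that the answer depends on an interval the plan does not name.
- **The 68% at 37 evaluable is a sawtooth trough.** At 38, exact and Wilson both give 79.9%. This is right, so 37 should not be quoted without 38 beside it.
- **The 15% loss may not suit this endpoint.** It is an allowance to the end of the study at day 30, while leakage is observed over 7 days of wear, and subjects withdrawn before application are replaced. This is fair, and the loss-adjusted figures are therefore assumptions.
- **Choosing the exact interval is a preference.** Partly so: Wilson would also be defensible. The exact interval matches the Exact test already named in section 10.4.1, and the essential point is that one method is named.
- **The 22 knee subjects are a closed cohort.** Their power figure informs no remaining recruitment decision, so including it is optional.

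**Conclusion.** The statement is wrong as written and should be corrected. At the plan's own 85% rate, 10 subjects give 19.7% power with the exact or Wilson interval and 54.4% with Wald, not 80%. About four times as many are needed: 45 evaluable for exact power to stay at 80%, 40 for Wilson and 34 for Wald.

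The consequence is limited. The primary abdominal analysis is adequate, with 96.8% exact power at 66 evaluable and 93.2% at 56. The 44-subject subset sits at about 80% with no reserve if the exact interval is used, and at 89% with Wilson or Wald.

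These results assume a true rate of 85% and independent subjects. The rows for 37 and 56 also assume that the 15% loss applies to leakage.

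**What to change.** 1. In section 11.1, delete the 10-subject, 80% power statement for leakage and replace it with text such as: *Assuming 85% of subjects have no exudate leak, and using the exact (Clopper-Pearson) two-sided 95% confidence interval, the power for the lower limit to exceed 65% is 97% with 66 evaluable abdominal subjects (93% with 56, if 15% are lost) and 79% with 44 evaluable (80% with 38, 68% with 37). Power is held at or above 80% from 45 evaluable subjects.* The figure for the 22 knee subjects, 58%, may be added for completeness.
2. In section 10.4.1, name the same exact interval for the 65% check. If another interval is preferred, name it and restate the power to match.
3. If the 70% sentence in section 11.1 is kept, either label it as expected precision (exact lower limit 72.6% at 38/44 leak-free, 69.9% at 37/44) or give its exact power (50% at 44, 67% at 56, 82% at 66).

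The 10-subject figure for wear time needs no change. Enrolment and procedures are unaffected. The only cost is a less favourable stated figure for the version 8.0 subset.

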## CONFIDENTIAL AND PROPRIETARY

This document contains information that is confidential and proprietary to Smith & Nephew PLC and Smith & Nephew, Inc. and is intended for use only by Smith & Nephew and its manufacturer. It shall not be reproduced or copied in whole or in part, nor shall the contents be disclosed by any means without prior written permission from Smith & Nephew, nor shall anyone make any use of it that is contrary to the expressed or implied wishes of Smith & Nephew.

[REDACTED] - [REDACTED] - [REDACTED]

**Clinical Protocol - Device****Pre-Registration Clinical  
Study**

Study Number:  
CT1705POB  
Version:9.0 04Aug2021  
Page: 91 of 221

$$H_0: \mu - \mu_0 \leq 0$$

$$H_a: \mu - \mu_0 > 0$$

In the stated hypothesis,  $\mu$  the mean [REDACTED] pump dressing wear time and  $\mu_0$  represents the literature derived value (4.6 days). A one-sided (one sample) t-test with alpha = 0.025 will be used to evaluate the hypothesis for each specialty. Based on the expected mean dressing wear time of 7 days, literature derived value of 4.6 days, and a standard deviation of 2.25 days, 80% power and 2.5% significance level, a sample size of 10 subjects per specialty is adequate to perform the above the hypothesis separately for each specialty cohort. Therefore, the planned forty-four subjects per specialty cohort are adequate to conclude that the [REDACTED] [REDACTED] system is strictly not worse (lower) than the literature derived value for each speciality individually. Further, with the planned 44 subjects per specialty, a dressing wear time below 6.0 days could be excluded for each specialty individually for the [REDACTED] device, represented by the lower limit of the 95% confidence interval lying above 6.0 days, based on assumptions previously listed; one-sided t-test with 80% power, 2.5% significance level, with a standard deviation of 2.25 days and assumed 7 day wear time of the [REDACTED] device.

No adjustment to the sample size calculations will be made to account for interim report related to safety review. The sample size was estimated using nQuery Advisor 4.0 and statistical software SAS Version 9.4.

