## **8 STUDY DESIGN**

### **8.1 Study Design**

This study is a prospective, multi-centre, non-randomised, non-blinded, single arm follow-up study to assess clinical performance and safety of [REDACTED] It is anticipated that up to 6 sites will participate within the UK.

The treatment phase will be 7 days post-surgery with a study follow-up period up to 30 days for assessment of complications. Seven days of therapy has been chosen as the length of time to assess device performance with use in real clinical conditions, since this is the length of time one system will operate and previous studies involving

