**9 STUDY PROCEDURES****9.1 Visits and Examinations****9.1.1 Summary****Figure 3 Study Procedures by Visit**

Schedule of events	Pre-Operative Data (Up to 6 weeks pre-surgery )	Operative Data	Baseline Post-Operative Data (within 24 ± 3 hours)	Dressing Inspection 4 ± 1 day	End of Therapy Assessment 7 days	Day 14 FU (14 (± 3) days)	Exit Visit Day 30 FU (30 (± 3) days)	Unscheduled Visit or Early Exit
Informed Consent	x							
Inclusion/Exclusion	x	x						
Demographics/Vital Signs/Medical History/History of Substance Use	x							
Concomitant Medication Check	x	x	x	x	x	x	x	x
Subject Comfort Level and VAS Pain Score				x	x			
Acceptability of NPWT system to Subject					x			
Assessment of NPWT application by Clinician		x						
Acceptability of NPWT system to Clinician					x			

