### **9.1.6 End of Therapy Assessment (7 days unless therapy is to be stopped sooner due to clinical need)**

1. Record date and treatment setting. If outpatient, and not previously recorded, record date of previous discharge.
2. If therapy is being discontinued prior to 7 days, record reason (e.g. [REDACTED] NPWT system removed, treatment interrupted for 24 hours or

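### The 80% power to exclude a mean wear time below 6.0 days (Section 11.1) rests on a mean of 7 days with SD 2.25, a pair not attainable if wear ends at about day 7

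*Combined protocol and SAP*

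**What the plan says.** Section 11.1 takes a literature mean wear time of 4.6 days with SD 2.2539 and projects that the new system "will have a mean dressing wear time of 7 days with similar distribution to the literature value". Two power statements follow, both for a one-sided one-sample t-test at 0.025:

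- 10 subjects per specialty suffice against 4.6 days.
- With 44 per specialty, "a dressing wear time below 6.0 days could be excluded for each specialty individually". The basis given is 80% power "with a standard deviation of 2.25 days and assumed 7 day wear time of the" device.

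Section 11.2 says that Phase 2 "will be powered according to previous sample size". It gives 44 new abdominal subjects and 66 in all, and no new wear-time assumption.

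On how long a system is worn:

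- Section 8.1: "The treatment phase will be 7 days post-surgery with a study follow-up period up to 30 days". Seven days was chosen "since this is the length of time one system will operate".
- Section 9.1.1, Figure 3: the visit is headed "End of Therapy Assessment 7 days", with no window, although the day 4, 14 and 30 visits have one.
- Section 9.1.6: the visit is at "7 days unless therapy is to be stopped sooner due to clinical need", and the system is removed there.

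**The concern.** The plan moves the mean from 4.6 to 7 days and keeps the spread of the old distribution. If 7 days is about the longest a system is worn, the mean can equal 7 only when nearly every system reaches day 7, and then the spread is close to zero. Any early removal pulls the mean below 7 unless other systems stay on past day 7. Section 7.8.1 foresees early ends to treatment (removal, pump failure, a dressing that falls off, a lost seal), so some early removals should be expected.

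At stake is a numerical assurance in the sample-size section of a study meant to support CE marking. A reader may take the 80% as a property of the design, when it depends on an early-removal pattern that the plan does not describe.

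**Working it through.** **Inputs.** Mean 7, SD 2.25, reference values 4.6 and 6.0, one-sided 0.025, n = 10 and 44, and 15% loss (all Section 11.1); 66 abdominal subjects in total (Section 11.2).

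**1. The plan's own figures.** Power is the probability that a noncentral t with n-1 degrees of freedom and noncentrality (7 - reference) x sqrt(n) / 2.25 exceeds the 97.5% point of central t.

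- Against 4.6, n = 10: noncentrality 2.4 x 3.162 / 2.25 = 3.37; power 85.0%.
- Against 6.0, n = 44: noncentrality 1.0 x 6.633 / 2.25 = 2.95; power 82.2%. The smallest n reaching 80% is 42 (80.3%).

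Both statements reproduce.

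**2. The planned loss.** Section 11.1 needs 38 subjects for pressure and enrols 44 to allow for 15% loss. The 6.0-day sentence uses all 44. After loss, 0.85 x 44 = 37.4 and 0.85 x 66 = 56.1. On the plan's own mean and SD, power against 6.0 is 74.9% at 37, 76.1% at 38, 90.4% at 56 and 94.5% at 66.

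**3. Can mean 7 and SD 2.25 occur together?** A variable on [0, c] with mean m has variance of at most m(c - m). The plan's variance is 2.25² = 5.0625.

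- c = 7, m = 7: the largest variance is 0.
- c = 7, SD 2.25: m(7 - m) ≥ 5.0625 gives m ≤ (7 + sqrt(49 - 20.25)) / 2 = 6.18.
- Mean 7, SD 2.25: 7(c - 7) ≥ 5.0625 gives c ≥ 7.72.
- c = 8, the superseded day-7 window of plus or minus one day recorded in the Amendment 8 log: the largest SD at mean 7 is sqrt(7 x 1) = 2.65, so the pair is possible. Let Y = wear - 7, so E(Y) = 0 and E(Y² + 7Y) = 5.0625. Y² + 7Y is at most 0 when Y ≤ 0 and at most 8 when 0 < Y ≤ 1. Hence the share worn past day 7 is at least 5.0625 / 8 = 63.3%.

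**4. Power under a 7-day limit.** The documents give neither the share nor the timing of early removals, so these are assumptions. A share p comes off early, uniformly over days 0-7 or over days 3-7; the rest reach day 7. The true means are 7 - 3.5p and 7 - 2p. Success means that the lower limit of the t-based 95% CI exceeds 6.0 (simulated, 400,000 replicates).

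| Early removals | n | 10% | 15% | 20% | 30% |
|---|---|---|---|---|---|
| Days 0-7 | 37 | 78% | 51% | 27% | 5% |
| Days 0-7 | 44 | 84% | 56% | 29% | 4% |
| Days 0-7 | 56 | 90% | 63% | 33% | 4% |
| Days 3-7 | 37 | 99.7% | 98% | 90% | 56% |
| Days 3-7 | 44 | 99.9% | 99% | 94% | 62% |
| Days 3-7 | 56 | 100% | 99.8% | 98% | 72% |

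At 30% over days 0-7 the true mean is 7 - 1.05 = 5.95, so 6.0 should not be excluded there. At n = 44, 80% power holds up to about 11% early removals (days 0-7) or 25% (days 3-7).

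**5. The planned test against 4.6 days.** In the less favourable case (30% early, days 0-7), power is 95.3% at n = 37, 97.7% at 44 and 99.4% at 56; with days 3-7 it is 100%. The 10-subject statement is itself conditional: at n = 10, power over days 0-7 is 91/83/72/51% for p = 10/15/20/30%.

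**The case against.** A reader might infer that the schedule makes the pair impossible and that the 80% has no basis at all. The documents do not go that far:

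- No section says that wear past day 7 cannot happen. Section 7.7 expects some late returns, Section 10.4.1 has a category for 7 days or more, and Section 9.1.9 still speaks of a visit window for this assessment.
- Part of the wear-time data source is redacted, and system life is not the same thing as dressing wear.
- Section 11.1 is headed as pre-interim and was written under the wider day-7 window, where the pair is possible. Section 11.2 does not repeat the 6.0-day sentence, so its carry-over to Phase 2 is an inference.
- The sentence names its own mean and SD.

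These points stand, and they make the conclusion conditional on wear ending at about day 7. They do not supply what the pair needs: some wear of at least 7.72 days and, even with an 8-day limit, most systems worn past day 7. No section plans that. Naming the assumptions does not make them fit the schedule.

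A reader might also infer that the wear-time endpoint is underpowered. That is not supported either: at n = 44 with 10% early removals over days 0-7, power is 84%, close to the plan's figure, and with later removals it is higher. The loss point is limited too, because the 15% is loss by study end and wear time is known by day 7.

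**Conclusion.** The point holds, conditionally, and is minor. If wear ends at about day 7, mean 7 with SD 2.25 is not attainable, and the stated 80% for excluding 6.0 days is unsupported for subjects on the current schedule. The error could run either way: under the assumed removal patterns, power at n = 44 runs from 4% to 99.9%. Separately, and on the plan's own inputs, the 44-subject set falls to 75-76% after the planned loss, while the 66-subject abdominal set keeps 90%.

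This is a faulty input assumption in a supplementary power statement; the plan's arithmetic is right. The sample size of 44 comes from the pressure endpoint, and the formal wear-time test is against 4.6 days. Neither changes. The conclusion rests on reading the 7-day schedule as an approximate upper limit on wear.

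**What to change.** In Section 11.1, delete the 6.0-day sentence. Alternatively, restate it with wear bounded at about 7 days, a stated range for the share and timing of early removals, and the planned loss (37 of 44 for the v8.0 subset, 56 of 66 for the primary abdominal analysis). Put a matching note in Section 11.2. Possible wording:

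*Wear time is limited to about 7 days, so its mean is below 7 if any system is removed early. If [x-y]% are removed early, at [timing], the probability that the lower 95% limit exceeds 6.0 days is [a-b]% with 56 subjects and [c-d]% with 37.*

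Do not simply strike the mean and SD, since they are the only wear-time justification for the 4.6-day test. Restate that justification on the same bounded distribution; with up to 30% early removals, power is about 95% or more at n = 37 and about 98% or more at n = 44.

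The cost is wording in two sections, with no new data and no change to sample size or tests. The sponsor has to commit to an early-removal range, and the figure becomes openly conditional on it.
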